10.4 Unusual Failure in Efficacy

Unusual Failure in Efficacy is defined as failure of a health product to produce the expected/intended effect, which may result in an adverse outcome for the patient, including an exacerbation of the condition for which the health product is being used. One example of unusual failure in efficacy is a previously well-stabilized condition that deteriorates when the patient changes to a different brand or receives a new prescription. Another example of a case that should be reported on an expedited basis is a life-threatening infection where the failure in efficacy seems to be due to the development of a newly resistant strain of bacterium previously regarded as susceptible.

Any unusual failure in efficacy reported during the conduct of the study should be immediately reported to an Allergan Inc. representative and recorded in the appropriate CRFs.

The Investigator must:

1. Notify Allergan Inc. immediately. For Emergency Phone Numbers see front of protocol. Fax completed Unusual Failure in Efficacy reporting form to: [REDACTED]
2. Obtain and maintain in his/her files all pertinent medical records, information, and medical judgments from colleagues who assisted in the treatment and follow-up of the subject.

10.5 Serious Adverse Events

An SAE is any AE that either led to death; resulted in a life-threatening illness or injury; resulted in a permanent impairment of a body structure or a body function; required in-patient hospitalization or prolongation of existing hospitalization; resulted in medical or surgical intervention to prevent permanent impairment to body structure or a body function; led to fetal distress, fetal death or a congenital abnormality or birth defect.

Pre-planned surgeries or procedures for pre-existing, known medical conditions for which a subject requires hospitalization are not reportable as an SAE. Any pre-planned surgery or procedure should be clearly documented in the site source documents by the investigator at the time of the subject's entry into the study.

NOTE: Allergan considers all cancer AEs as SAEs. Pregnancy by itself is not generally considered an AE. The occurrence of an adverse pregnancy outcome may constitute an SAE, making the collection of pregnancy-related data and pregnancy outcomes valuable. Inpatient hospitalization for a normal vaginal delivery or elective abortion of a normal fetus does not constitute a SAE. If no serious injury occurred to the mother or fetus, then there is no reason to qualify pregnancy in the setting of hospitalization as a SAE. Accidental, therapeutic, or

spontaneous abortion should always be classified as a SAE and expeditiously reported to the Sponsor. Some examples of pregnancy related SAEs are, but not limited to the following conditions: placental abruption, placenta previa, pre-eclampsia, prematurity, fetal death, congenital anomaly or birth defects.

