10.6 Unanticipated Serious Adverse Device Effects

An unanticipated adverse device effect (USADE) is any device-related SAE that meets one or more of the following criteria:

- Is not identified in nature, severity, or frequency in current literature on the product
- Is life-threatening, even if temporary in nature
- Results in permanent impairment of a body function or permanent damage to a body structure
- Necessitates medical or surgical intervention to preclude permanent impairment of a body function or permanent damage to a body structure

Also considered an USADE is any device malfunction that would be likely to cause or contribute to a death or serious injury if the malfunction were to recur. The investigator will notify Allergan within 24 hours of any device malfunction and a representative will provide instruction for the return of any faulty syringe for evaluation.

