10.7 Assessment of Adverse Events

10.7.1 Severity

Assessment of severity of an AE will be rated according to the definitions in Table 10.1 and the worst grade documented. The investigator will review these definitions with the subject for use when completing the subject diary. For events reported on the AE eCRF, eg, ISRs that persist beyond the diary period and other AEs, the investigator will determine the severity classification based on these definitions, his/her experience in the use of dermal fillers and/or the subject's description of the event.

The term "severe" is used to describe the intensity of an AE; the event itself could be of relatively minor clinical significance (eg, "severe headache"). This is not the same as "serious." Seriousness of AEs is based on the outcome of an AE and usually associated with events that pose a threat to a subject's life or functioning.

Table 10.1 Classification of Adverse Events by Intensity

Grade 1 (Mild)	The symptom is barely noticeable to the study subject and does not influence performance or functioning. Concomitant medication is not ordinarily indicated for relief of mild AEs.
Grade 2 (Moderate)	The symptom is of sufficient severity to make the study subject uncomfortable and to influence performance of daily activities. Concomitant medication may be indicated for relief of moderate AEs.
Grade 3 (Severe)	The symptom causes severe discomfort, sometimes of such severity that the study subject cannot continue in the study. Daily activities are significantly impaired or prevented by the symptom. Concomitant medication may be indicated for relief of severe AEs.
Not applicable	In some cases, an AE/ISR may be an “all-or-nothing” finding that cannot be graded.

Abbreviations: AE = adverse event, ISR = injection site reaction.

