10.9 Serious Adverse Event Reporting

10.9.1 Reporting Requirements

Any SAE occurring during the study period (beginning with informed consent) and through 30 days after study exit must be reported within 24 hours to Allergan on 2 SAE forms. The drug, and device SAE forms must be recorded and e-mailed per this protocol section (including to the SkinMedica Safety Contact below from V7 to V12). All subjects with an SAE must be followed up and the outcomes reported.

The principal investigator must supply Allergan and the REB with any additional requested information (eg, hospital discharge summary, autopsy reports and terminal medical reports) only upon request. Allergan will evaluate all SAEs for both drug and device. Device SAEs will be documented in writing as to whether they meet the definition of an USADE. These will be reported to all participating investigators, the regulatory authorities, and the REB.

[figure not shown]
In the event of an SAE, the investigator must:

1. Notify Allergan immediately (within 24 hours) using the SAE reporting forms. Emergency phone numbers and relevant Allergan personnel contacts are below.
2. Obtain and maintain in his/her files of all pertinent medical records, information, and medical judgments from colleagues who assisted in the treatment and follow-up of the subject.
3. Provide Allergan with a complete, written case history (AE report form), including copies of supporting reports (eg, progress notes, laboratory reports), upon request and a statement from the investigator as to whether the event was or was not related to the use of the investigational drug or device.
4. Promptly inform the governing REB of the SAE, if it is device-related, as required by the REB, local regulations, and the governing health authorities.

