11.1 Adverse Events

All Adverse events (AEs) will be classified by Primary System Organ Class (SOC) and Preferred Term (PT) according to the Medical Dictionary for Regulatory Activities (MedDRA) Version 21.0 or newer.

TEAE is defined as an AE that was not present prior to treatment with investigational products but appeared following treatment or was present at treatment initiation but worsened after treatment or become SAE.

An SAE is defined as any AE that either led to death; resulted in a life-threatening illness or injury; resulted in a permanent impairment of a body structure or a body function; required in-patient hospitalization or prolongation of existing hospitalization; resulted in medical or surgical intervention to prevent permanent impairment to body structure or a body function; led to fetal distress, fetal death or a congenital abnormality or birth defect.

AE summary tables will be presented for TEAEs only and will include the following:

- All TEAEs
- TEAEs related to study drug
- TEAEs leading to study discontinuation
- Serious/Severe TEAEs
- Serious/Severe TEAEs related to study drugs
- TEAEs leading to death.

All TEAEs will be summarized by SOC, PT and treatment group using frequency counts and percentages (i.e., number and percentage of subjects with an event). In addition, an overall summary for the categories above will be prepared by treatment group and overall.

All TEAEs will be summarized by SOC, PT, maximum severity, and treatment group using frequency counts and percentages (i.e., number and percentage of subjects with an event)

An AE will be considered as related if the event is Possibly, Probably or Definitely related. If the relationship to study drug is missing, the AE will be treated as related. For AE with severity missing, the missing severity will be imputed as severe.

For the incidence at the subject level by SOC and PT, if a subject experiences more than one event within the same SOC and PT, only one occurrence will be included in the incidence. For the incidence at the subject level by SOC, PT, and severity, if a subject experiences more than one event within the same SOC and PT, only the most severe occurrence will be included in the incidence.

For the incidence at the subject level by SOC, PT, and relationship to investigational product, if a subject experiences more than one event within the same SOC and PT, only the most related occurrence will be included in the incidence.

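### The SAE list has no criterion for significant but non-permanent disability and none for medical judgement, so a narrow class of disabling reversible reactions gets neither 24-hour reporting nor SAE listing

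*Protocol*

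**What the plan says.** Protocol 10.1 and 10.2 define drug and device adverse events separately, but Protocol 10.5 sets one list of seriousness criteria for both. Besides death and adverse fetal outcomes, an event is serious if it:

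- threatened life;
- "resulted in a permanent impairment of a body structure or a body function";
- led to a hospital admission or lengthened a current stay; or
- "resulted in medical or surgical intervention to prevent permanent impairment to body structure or a body function".

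A note adds all cancers and certain pregnancy outcomes. SAP 11.1 opens its own definition with "An SAE is defined as any AE that either led to death" and then gives the same criteria.

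Protocol 10.7.1, in explaining how severe differs from serious, says that seriousness is "usually associated with events that pose a threat to a subject's life or functioning".

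Under Protocol 10.9.1, SAEs from consent "through 30 days after study exit must be reported within 24 hours to Allergan on 2 SAE forms". Protocol 4.3 ends general AE collection at the last study visit, V12. SAP 11.1 lists all AEs and adds separate listings for serious AEs, AEs leading to discontinuation, and deaths.

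**The concern.** The operative list handles loss of function only through permanence, either as the outcome or as what an intervention was meant to avert. It has no entry for disability that is significant while it lasts but later resolves, and no entry that rests on medical judgement.

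This matters because the protocol itself treats functional loss as a relevant risk. Exclusion criteria 21 to 24 and 30 in Protocol 5.2 remove people with conditions that raise the risk of botulinum toxin exposure, weak target muscles, past facial nerve palsy, or neuromuscular disorders with signs such as ptosis and dysphagia. Protocol section 1 describes BELKYRA as cytolytic. A temporary functional deficit is a foreseeable kind of event here, and the sponsor's early warning depends on whether it is classed as serious.

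**Working it through.** No arithmetic applies: the point concerns the wording of a definition, and the plan gives no figure to reproduce. The check is to take one event type through every route to seriousness or expedited reporting. The event is a disabling reaction that later resolves and is managed without admission.

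1. **Life-threatening.** If it threatens life, it is an SAE under Protocol 10.5, with no need for permanence or admission.
2. **Intervention.** If it was treated in order to prevent permanent impairment, it is an SAE, again without permanence or admission.
3. **Neither.** Suppose it is observed, or treated only for symptoms. It is not fatal, not life-threatening, not permanent, not admitted and not treated to avert permanent harm. The cancer and pregnancy notes do not apply. No criterion is met, so it is not an SAE.
4. **USADE route (Protocol 10.6).** A USADE "is any device-related SAE that meets one or more of the following criteria", so it cannot bring in an event that is not already an SAE. The added provision for device malfunctions concerns the device and not a reaction as such.
5. **Other rapid-reporting routes.** Unusual failure in efficacy (10.4) and pregnancy (10.8.2) address different occurrences.
6. **SAP route.** SAP 11.1 repeats the criteria and adds none, so the analysis classifies the event in the same way.

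For an event in case 3, the consequences are:

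| Function | Rule | Result |
|---|---|---|
| 24-hour report to the sponsor | Protocol 10.9.1, triggered by SAE status | None |
| Serious-AE listing | SAP 11.1, restricted to serious AEs | Absent |
| Onset after V12 | AEs end at V12 (Protocol 4.3); SAEs run to 30 days after exit (10.9.1) | No stated route, unless it is an injection site reaction (10.3) |
| Recording during the study | Protocol section 10: all AEs on the eCRF | Kept |
| Tables | SAP 11.1: all TEAEs, by maximum severity, and a combined serious-or-severe category | Kept if treatment-emergent; in the combined category if graded severe |
| Listings of all AEs and of discontinuations | SAP 11.1 | Kept; in the latter if it led to discontinuation |
| Ethics board | Protocol 10.8.1: related and unexpected AEs, as the board requires | Possible; no 24-hour limit stated |

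Protocol 10.8.1 also requires follow-up of AEs still ongoing at exit, but that does not reach events that start afterwards.

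Set beside 10.7.1, the operative list is the narrower text. A case 3 event may well threaten functioning in the sense used there, yet it meets no criterion in 10.5.

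**The case against.** The best defence is that the list already reaches the worst reversible events. Respiratory compromise that threatens life is serious, and so is any reaction treated to avert lasting damage. This stands, and it rules out a tempting stronger reading: that loss of function counts only when permanent, or that a reversible reaction managed as an outpatient can never be serious. The same sentence of Protocol 10.5 contradicts both.

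It can also be said that nothing is hidden. Such events are recorded, related ones are followed until resolved or stable, and they appear in the TEAE tables and the listing of all AEs. That also stands. A reader might infer that disabling events could disappear from the results behind a zero SAE count; for events during the study the documents do not support that. Even so, the severity tables are only a partial substitute. Protocol 10.7.1 itself says that a severe event may be clinically minor and that severe does not mean serious. No listing is set aside for severe events.

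Third, 10.7.1 is explanatory and hedged, and a threat to functioning can partly be met by the intervention criterion. This is fair: it is not a rival definition. It does show that the authors' description of seriousness does not require permanence, while the list gives no way to act on that where nothing was done to avert permanent harm.

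Fourth, SAP 11.1 foresees AEs that later become SAEs, so a report can follow once a criterion is met. That helps when an event worsens or proves permanent, but not when it resolves.

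Finally, neither document contains a disability or medical-importance criterion against which 10.5 could be called wrong. The point therefore rests on the mismatch with 10.7.1 and on the consequences traced above, not on an outside standard.

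**Conclusion.** The point holds for a defined class: reactions that are disabling and reversible, not life-threatening, not admitted, and not treated to prevent permanent impairment. These are non-serious under both documents. What is lost is the 24-hour report, SAE classification and the serious-AE listing, plus any stated collection route when onset is after V12 and the event is not an injection site reaction. The event itself is not lost if it occurs during the study.

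No number can be put on this. The documents give no expected frequency for such events, and dividing one event by the planned enrolment would only restate the sample size. The conclusion assumes that sites apply the list in 10.5 as written and treat the wording in 10.7.1 as explanation. If sites already report more widely, the practical gap is smaller, but it then varies by site. The primary endpoint is unaffected. The change is worth making because it is cheap and concerns safety oversight.

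**What to change.** Add two criteria to the SAE definition in Protocol 10.5 and, identically, in SAP 11.1, for both drug and device events:

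- *resulted in persistent or significant disability or incapacity, whether or not permanent*;
- *is otherwise medically important in the investigator's judgment*.

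This reconciles both definitions with Protocol 10.7.1. Events that meet the new criteria would fall under the existing 24-hour rule and the 30-day post-exit window, so no separate change is needed for those starting after V12.

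The cost is a protocol amendment and a SAP amendment (Protocol 11.7) and a few more SAE reports. There may also be more USADE reports, since USADEs are drawn from device-related SAEs and, under Protocol 10.9.1, go to all participating investigators, the regulatory authorities and the ethics board. If subjects have already been treated, AEs already recorded should be checked against the amended list so that the SAE listing uses one definition throughout.

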10.6 Unanticipated Serious Adverse Device Effects

An unanticipated adverse device effect (USADE) is any device-related SAE that meets one or more of the following criteria:

- Is not identified in nature, severity, or frequency in current literature on the product
- Is life-threatening, even if temporary in nature
- Results in permanent impairment of a body function or permanent damage to a body structure
- Necessitates medical or surgical intervention to preclude permanent impairment of a body function or permanent damage to a body structure

Also considered an USADE is any device malfunction that would be likely to cause or contribute to a death or serious injury if the malfunction were to recur. The investigator will notify Allergan within 24 hours of any device malfunction and a representative will provide instruction for the return of any faulty syringe for evaluation.

10.7 Assessment of Adverse Events

10.7.1 Severity

Assessment of severity of an AE will be rated according to the definitions in Table 10.1 and the worst grade documented. The investigator will review these definitions with the subject for use when completing the subject diary. For events reported on the AE eCRF, eg, ISRs that persist beyond the diary period and other AEs, the investigator will determine the severity classification based on these definitions, his/her experience in the use of dermal fillers and/or the subject's description of the event.

The term "severe" is used to describe the intensity of an AE; the event itself could be of relatively minor clinical significance (eg, "severe headache"). This is not the same as "serious." Seriousness of AEs is based on the outcome of an AE and usually associated with events that pose a threat to a subject's life or functioning.

Table 10.1 Classification of Adverse Events by Intensity

Grade 1 (Mild)	The symptom is barely noticeable to the study subject and does not influence performance or functioning. Concomitant medication is not ordinarily indicated for relief of mild AEs.
Grade 2 (Moderate)	The symptom is of sufficient severity to make the study subject uncomfortable and to influence performance of daily activities. Concomitant medication may be indicated for relief of moderate AEs.
Grade 3 (Severe)	The symptom causes severe discomfort, sometimes of such severity that the study subject cannot continue in the study. Daily activities are significantly impaired or prevented by the symptom. Concomitant medication may be indicated for relief of severe AEs.
Not applicable	In some cases, an AE/ISR may be an “all-or-nothing” finding that cannot be graded.

Abbreviations: AE = adverse event, ISR = injection site reaction.

10.7.2 Relationship to Study Product

A determination will be made, by the investigator, of the relationship, if any, between an AE and any study product, anesthesia employed, the study device, or the injection procedure, as applicable, using the guidelines presented in Table 10.2.

Table 10.2 Guidelines for Determining the Relationship Between Adverse Event and the Study Product

Highly Probable	This causal relationship is assigned if the AE starts a reasonable time after the administration of study product, stops/improves when the study product is stopped, and could reasonably be explained by known characteristics of the study product.
Probable	This causal relationship is assigned when the AE starts a reasonable time after the administration of study product, stops/improves when the study product is stopped, and could not be reasonably explained by known characteristics of the subject’s clinical state.
Possible	This causal relationship is assigned when the AE starts a reasonable time after the administration of study product, but could be produced by the subject’s clinical state or other modes of therapy administered to the subject.
Not Related	This causal relationship is assigned when the time association or the subject’s clinical state is such that the study product was not likely to have had an association with the observed AE.

Abbreviations: AE = adverse event.

10.8 Adverse Events and Pregnancy

MAHs are expected to follow up all pregnancy reports from health professionals and consumers where the embryo/fetus could have been exposed to one of its health products. For consumer reports, it is appropriate to seek permission to only follow up with the health professional. The MAH must apply all principles outlined in this guidance document and the Regulations pertaining to reporting requirements, including determination of seriousness and

minimal criteria for submitting an AR report. Reports of pregnancy exposure with no associated adverse reactions should not be reported as ARs. When an active substance, or one of its metabolites, has a long half-life, this should be taken into account when considering whether a fetus could have been exposed (e.g., if health products taken before the gestational period should be considered).

10.8.1 Adverse Event Follow-up

All AEs (including SAEs) must be recorded on the appropriate eCRF. All AEs that are treatment-related and unexpected (not listed as treatment-related in the current package insert or directions for use) must be reported to the governing REB as required by the REB, local regulations, and the governing health authorities. Any AE that is marked “ongoing” at the exit visit must be followed up as appropriate.

